Local authority	Number of social workers and family support workers in teams in the intervention group	Hold back for staff turnover (assume 15%)	Number of foster carers (including kinship carers) in the intervention group	Hold back for new foster carers (assume 10%)	Number of Kitbags for social workers in the fostering service	Total
Bexley	33	5	57	6	2	103
Haringey	28	4	100	10	2	144
Oxfordshire	120	18	119	12	4	273
Warwickshire	119	18	148	15	10	310
Total	300	45	424	43	18	830

Children and young people

Children and young people aged 4-18 years old who have an open case in May 2021 or whose case opens between May 2021 and December 2021 and supported by social workers and family support workers in eligible teams are eligible for the programme. Only those whose

case starts before December 2021 will be eligible to allow for the minimum number of sessions to feasibly be delivered with a Kitbag before the evaluation period concludes (May 2022).

The number of children and young people who are classified as children in need (according to the Department for Education’s broad definition including children on a child in need plan, child protection plan and children in care) across these four local authorities is approximately 13,000. We estimate that there are approximately 9300 eligible children and young people across the four local authorities (henceforth we refer to them as the population).⁶

Table 3: Number of children in need in Bexley, Haringey, Oxfordshire and Warwickshire between 2019 and 2020

Local authority	Number of children in need at 31 March (2019)	Number of children in need at 31 March (2020)
Bexley	1594	1757
Haringey	2073	2284
Oxfordshire	4511	4750
Warwickshire	3914	4073
Total	12092	12864

Recruitment

Social workers / family support workers

Social workers will be identified from their membership in eligible teams, as per the HR IT systems of the local authorities. The social workers and family support workers will be asked to provide their informed consent before participating in the primary data collection (survey, interviews). They will also be notified of the use of their absence data in the email inviting them to participate in the survey at T6 (prior to the data sharing) and of their rights in relation to the processing.

Children and young people

Children and young people will be identified as eligible by their allocation to a social worker in an eligible team.

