¹² Lundh, L.G., Wangby-Lundh, M., & Bjarehed, J. (2008). Self reported emotional and behavioral problems in Swedish 14 to 15-year-old adolescents: A study with the self-report version of the Strengths and Difficulties Questionnaire. *Scandinavian Journal of Psychology*, 49, 523–532.

¹³ <https://youthinmind.com/products-and-services/sdq/>

¹⁴ Scoring the Strengths & Difficulties Questionnaire for age 4-17. (2014).

<https://www.ehcap.co.uk/content/sites/ehcap/uploads/NewsDocuments/236/SDQEnglishUK4-17scoring-1.PDF#page=4>

¹⁵ Goodman A, Lamping DL, Ploubidis GB. When to use broader internalising and externalising subscales instead of the hypothesised five subscales on the Strengths and Difficulties Questionnaire (SDQ): data from British parents, teachers and children. *J Abnorm Child Psychol*. 2010 Nov;38(8):1179-91. doi: 10.1007/s10802-010-9434-x. PMID: 20623175.

¹⁶ Van den Broeck, A., Vansteenkiste, M., De Witte, H., Soenens, B., & Lens, W. (2010). Capturing autonomy, competence, and relatedness at work: Construction and initial validation of the Work-related Basic Need Satisfaction scale. *Journal of Occupational and Organizational Psychology*, 83(4), 981-1002.

¹⁷ Stanton, J. M., Balzer, W. K., Smith, P. C., Parra, L. F., & Ironson, G. (2001). A General Measure of Work Stress: The Stress in General Scale. *Educational and Psychological Measurement*, 61(5), 866–888. <https://doi.org/10.1177/00131640121971455>

more stress. The sixth secondary outcome measure is the mean of the responses for the 8 items¹⁸ where “no” is coded as 0, “?” is coded as 1.5 and “yes” is coded as 3 (2vi)¹⁹.

2iv) Days attended

The hypothesised lower stress may lead to fewer sick days of social workers. We measure this over the entire intervention period from T1 to T13. Instead of measuring the number of sick-days, we will instead measure the number of ‘days attended’ in work. This allows us to include social workers who leave their posts over the course of the trial - these individuals will be classified as absent every day after they leave. Excluding these participants from the absence analysis would risk biasing the results, as individuals’ likelihood to leave is correlated with their rate of sickness absence. The number of days not attended may include holidays and parental leave in addition to sickness absence. If possible, we will control for the number of days of holiday and parental leave.

Foster and kinship Carer Outcomes

2v) Self-efficacy

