- for social workers and family support workers: the social worker or family support worker was a member of a team assigned to the intervention at point of randomisation and 0 else;
- for foster / kinship carers: the carer cares for a child or young person whose case is held at the point the foster carer enters the sample, by a social worker who is a member of a team assigned to the intervention at point of randomisation and 0 otherwise.

Although there is some turnover of social workers, family support workers and foster carers, about 80% of those at T0 (April 2021) will still be working with the local authority at T13 (May 2022), and so 80% will have received the full 12 months of the intervention. Binarising the treatment seems a reasonable proxy in this case.

For the outcomes relating to children, treatment is coded as a binary variable. When children enter the sample, at either the point of randomisation, or the point they become eligible (e.g. their case opens and meets other criteria) they will be allocated to treatment if the team of their allocated social worker was randomised to treatment.

Covariates

Including control variables increases the precision of the estimate. In each regression, we control for a number of relevant covariates. We outline different categories of covariates below.

Site effects

We include site fixed effects but not site-treatment interaction terms.

Previous outcome measures

We control for the previous measurements of the outcome variable where data is available. For the survey-based measures for social workers, family support workers and foster carers, the same measures will be asked at T6 (October 2021) and T13 (May 2022), and for administrative data we expect previous values to be available. For the outcomes of the CYP and parents / carers (including kinship carers), the previous measure of the outcome will be at T0 (April 2021) or when they entered services if they entered services after T0 (April 2021).

Other covariates

For CYP outcomes (primary outcome i) and secondary outcome i)), we include the following vector of individual-level covariates:

- gender (coded as male, female, or other/missing)
- age group (4-11, 12-17, 18 years, or missing with 4-11 as the reference category)
- ethnicity (Asian / Asian British, Black / African / Caribbean / Black British, Mixed / Multiple ethnic groups, Other ethnic group, White, missing; with the majority group as the reference category)

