- **Personnel:** the cost of hiring agency workers to conduct day-to-day work so that social workers / family support workers could attend the workshops (if applicable)
- **Administration costs:** the cost of hiring additional staff to administer the programme

The costs will be reflective of the current context of Covid-19 restrictions. In some cases, this is likely to increase the costs e.g. distribution, and in other circumstances, it's likely to decrease the costs e.g. virtual workshops instead of in-person workshops.

Where there is additional work required but not sufficient to hire an agency worker or another member of staff, we shall report the additional time commitment in hours over the course of the year for the staff affected.

As well as these costs incurred over the duration of the programme, we shall report prerequisites (anything the local authority needed to run the programme but may already have e.g. laptops) and expected ongoing costs. Costs associated with the development of the programme and the evaluation e.g. the collection of data will be excluded.

Valuing benefits and disbenefits

Although administrative outcomes aren't the outcomes of most interest, we only include the administrative outcomes when valuing benefits as these are the benefits that are "cashable" to local authorities:

- De-escalation in children's social care status as a benefit
- Escalation in children's social care status as a disbenefit
- Number of social worker sick days averted (estimated by the coefficient on treatment in the regression of the number of days attended on treatment and covariates)

For the impact evaluation, we code de-escalation and escalation as a single outcome. But because there are different costs associated with each movement, we shall separately estimate the impact of Kitbags on the likelihood of moving between different levels of CSC intervention. For each movement, we calculate the total monetised benefit:

- Unmonetised benefit = ATE (i.e. the coefficient on the treatment dummy) x number children randomised to the intervention group
- Monetised benefit: total unmonetised benefit x cost (averted) / child

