The outcomes do not double count any benefits and we only include outcomes that are significant at the 5% level. We request data from the local authorities on the average costs of supporting a child at each level of CSC intervention and use this to determine the "cost (averted)" value. Whilst placement costs vary, we use an average for simplicity. We sum the monetised benefits and disbenefits to arrive at a net benefit.

We do not monetise the other outcomes such as improved behaviour amongst children and young people. This is not to say that these outcomes aren't valuable but simply that there's less agreement on how to put a monetary value on these outcomes. We report a list of outcomes that are significant.

Discounting

Given that all the benefits and costs occur within the same financial year, we do not discount any of the benefits or costs.

Reporting

We report the benefit-cost ratio, and the net present value per child.

Ethics & Participation

An ethics application for this evaluation was submitted to WWCS's research ethics committee on 25th February 2021 with a favourable opinion given on 23rd March 2021.

Consent procedures

Information sheet contents

The information sheets will be tailored to the participant group and will detail the purpose of the project, why they have been invited to take part, what will happen if they take part, whether they have to take part, the possible risks, the possible benefits, the data handling, confidentiality and data protection, the right to withdraw their consent, how the project is funded, what will happen to the results of the project, contact details if they wish to ask further questions.

Social workers

Data collection from social workers will be via an online survey. The first page of the survey will be an information sheet and consent elicitation.

Impact Evaluation: Secondary Data Collection

Children and young people

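### The cost evaluation prices the days-attended coefficient as sick days averted although that outcome counts post-exit days as absence, and it admits only outcomes significant at 5% to the net benefit

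*Protocol*

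**What the plan says.** The front page and secondary outcome 4 of the Protocol ask about the number of sick days taken by social workers and family support workers. Under Outcome measures, section 2iv (Days attended), the measured variable becomes days attended. For staff who leave, "these individuals will be classified as absent every day after they leave". The section adds: "The number of days not attended may include holidays and parental leave in addition to sickness absence", and then "If possible, we will control for the number of days of holiday and parental leave". On the window it says "We measure this over the entire intervention period from T1 to T13".

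The Cost evaluation (Valuing benefits and disbenefits) takes the treatment coefficient from that regression as a benefit: "Number of social worker sick days averted (estimated by the coefficient on treatment in the regression of the number of days attended". It also plans separate estimates for each movement between levels of social care involvement. On what enters the sum it says "we only include outcomes that are significant at the 5% level". Benefits and disbenefits are then added to a net benefit, and a benefit-cost ratio and a net present value per child are reported.

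On turnover, the Analysis plan expects that "about 80% of those at T0 (April 2021) will still be working with the local authority at T13 (May 2022"). That figure pools social workers, family support workers and foster carers. The staff hold-back in Table 2 assumes 15%.

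**The concern.** There are two separate faults, and both act on the net benefit, the ratio and the net present value.

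The first is a change of quantity between the outcome definition and its valuation. A day after exit is not a sick day. The Participants section also foresees a replacement for a leaver, so a post-exit day does not carry the cost of a sick day. If Kitbag changes how many staff leave, that effect enters the benefit under the wrong name. Adjusting for holiday and parental leave does not cure this. Both are taken after randomisation, and a leaver takes less of them because of leaving. The adjustment therefore conditions on a consequence of leaving and does not remove the post-exit days.

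The second is the inclusion rule. A net benefit is an estimate, and setting each component to zero unless it passes a test distorts it. A non-significant rise in escalations, which is a cost, is dropped as readily as a non-significant saving. The components that pass are, on average, too large when power is low. No uncertainty is attached to the ratio.

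**Working it through.** The Protocol gives no sickness rate, unit cost of a sick day, effect size or ratio, so there is no figure of its own to reproduce.

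**Inputs from the Protocol.** Share leaving L: about 20% (Analysis plan), with 15% from the Table 2 hold-back as an alternative. Intervention-arm workers: 300 (Table 2). About 1,000 social workers in all (Data protection), or 500 per arm if split equally. Significance level: 5%.

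**Assumptions.** Working days D from 220 to 260. Exit times uniform over the window. Sickness rate s from 2% to 6% of days in post. A control arm as large as the intervention arm.

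**Step 1: post-exit days in each arm.** The mean per worker is L × D/2. With L = 0.20 this is 22 days (D = 220) to 26 days (D = 260), or 6,600 to 7,800 days over 300 workers.

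**Step 2: effect of a difference in leaving.** Days attended per worker = D × (1 − L/2) × (1 − s).
- Before the factor (1 − s), a 1-point difference gives 0.01 × D/2 = 1.1 to 1.3 days per worker, or 330 to 390 days over 300 workers.
- With equal s and leaving of 18% against 20%, the coefficient is +2.1 to +2.6 days. Recorded sick days averted are −0.04 to −0.16 per worker, because staff who stay longer also have slightly more time in which to be sick.
- With leaving equal in both arms, the difference is 0.

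**Step 3: can a sickness effect pass the 5% rule?** The variance of post-exit days is D² × (L/3 − L²/4). The standard error of the difference is SD × √(2/n). The figures are unadjusted and leave out clustering, sickness noise and the small factor (1 − s). Total sickness per worker is D × (1 − L/2) × s.

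| L | n per arm | SD (days) | SE (days) | 1.96 × SE (days) | As a share of all sickness, s = 6% / 4% / 2% |
|---|---|---|---|---|---|
| 20% | 300 | 52.4–61.9 | 4.28–5.05 | 8.4–9.9 | 71% / 106% / 212% |
| 15% | 500 | 46.3–54.8 | 2.93–3.46 | 5.7–6.8 | 47% / 71% / 141% |

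Even in the more favourable row, at the highest assumed sickness rate, the estimated effect must be about half of all sickness to count.

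**Step 4: the 5% rule on any component.** Let the estimate divided by its standard error be normal with mean m and variance 1, and c = 1.96. The expected counted value is m × P + φ(c − m) − φ(c + m), where P is the power.

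| Power | Expected counted / true | Average when counted / true |
|---|---|---|
| 10% | 0.34 | 3.4 |
| 20% | 0.45 | 2.2 |
| 50% | 0.70 | 1.4 |
| 80% | 0.90 | 1.13 |
| 90% | 0.95 | 1.06 |

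On average the rule understates a real effect. When it counts one, it overstates it.

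**The case against.** Coding leavers as absent is a reasoned choice. Section 2iv explains that leaving is correlated with sickness absence, so excluding leavers could bias the attendance comparison. That stands, and it supports days attended as a secondary outcome. It does not support calling its coefficient sick days averted.

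Several stronger readings are tempting, but the Protocol does not support them:
- A reader might infer that the ratio is simply wrong. The leaver term is zero in expectation unless leaving differs by arm, so what can be said is that a leaving effect, if there is one, would be priced as sickness.
- A reader might infer that the coefficient is mostly a turnover difference because leaving dominates the variance. A share of variance does not decide what a difference in means estimates. If Kitbag lowers sickness and leaves turnover unchanged, the expected coefficient reflects sickness. The variance costs power.
- A reader might treat a chance gap in turnover as bias in the ratio. A 2-point gap (2.6 days at D = 260) with a standard error of about 5 gives z of about 0.5. It is sampling error, and taken alone the 5% rule would drop it.
- A reader might say that the rule favours benefits. It zeroes non-significant benefits and harms alike.
- Four levels allow up to 12 directed movements, and 1 − 0.95¹² = 46% is the chance of at least one false inclusion if none is affected. This is only an upper illustration: the Protocol states no number of movements, and movements from the same level are not independent.

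Pricing sickness over time in post also has a weakness. Time in post is itself determined after randomisation, so part of the selection problem named in section 2iv returns. This is why retention must be reported beside it.

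**Conclusion.** The concern holds in this limited form. The cost evaluation fixes an estimator that does not measure what it is priced as, and an inclusion rule that distorts the sum. No other section of the Protocol corrects either.

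On the assumed working days and uniform exits, the first fault is worth 1.1 to 1.3 days per worker for each percentage point by which leaving differs between arms, and nothing in expectation if leaving is equal. Its actual size and direction cannot be known from the Protocol. On the same assumptions, noise from leavers makes a realistic sickness effect unlikely to reach the ratio at all. The second fault depends on power: a counted effect is overstated about 2.2-fold on average at 20% power and 1.13-fold at 80%. It is also not stated whether the 5% applies before or after the Hochberg adjustment of the secondary outcomes.

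This should be changed before the cost analysis. It does not affect the primary outcome.

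**What to change.** 1. Keep days attended as the secondary outcome, but do not price it as sickness.
2. In the cost evaluation, estimate sickness from recorded sick days over time in post, and name the unit cost to be used. Report retention by arm separately.
3. Do not adjust for holiday or parental leave taken after randomisation.
4. Enter all pre-specified movement and sickness estimates at their point values, significant or not. Give a bootstrap interval, resampling teams, for net benefit and for the ratio.

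The cost is a little more analysis. Sickness-absence data are already requested from the local authorities (Consent procedures). Leaving dates are also needed; section 2iv implies them, but the data request does not name them. The downsides are that sickness is seen only while staff are in post and that the interval will be wide.

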January 2021	Advisory Board meetings	UoS/IFF
January - March 2021	Site selection, engagement, set up meeting and work	All
March 2021	Ethics approval obtained	WWCS
March 2021	Randomisation of teams to kitbag	WWCS
April 2021	Kitbag leads identified and appointed	LA partners
Before data collection	Trial protocol drafted and published	WWCS
May 2021	Kitbag distribution	UoS/IFF

10th May 2021	Launch of project in 4 sites as one online event	UoS/IFF + LA partners
May 2021 - April 2022	Regular Kitbag use	LA partners
May 2022	Endline data collection	LA partners / WWCS
June - July 2022	Final analysis and report	WWCS
